3.1 Study Design

For the purpose of exploring the above objectives, the study will be conducted as a randomized, double-blind, sham-controlled dose escalation study in SARS-CoV-2 infected individuals with outpatient COVID-19 at two dosing schedules.

This study plans to enroll into two treatment arms within two escalating dose cohorts:

Volunteers meeting all inclusion criteria and none of the exclusion criteria will be randomized to the RD-X19 treatment arm or the sham treatment arm within each cohort in a 2:1 ratio (20 RD-X19 : 10 sham), according to a fixed schedule via a permuted block design and stratified by clinical site. Light will be administered twice daily locally to the mouth and throat only for four days for Cohort 1 and for seven days for Cohort 2.

The clinic visits will occur at:

- Visit 1 / Screening, Enrollment & Randomization

- Visit 2 / Day 2
- Visit 3 / Day 3
- Visit 4 / Day 5 (\pm 1 day)
- Visit 5 / Day 8 (\pm 1 day) / Early Termination (ET)

Assessments of treatment response will occur on study days 3 and 5, with a final determination of efficacy made on day 8 (inclusive).

Efficacy will be evaluated through evaluation of viral load through quantitation of SARS-CoV-2 mRNA by RT-qPCR and via quantitation of replication competent virus by viral titer. Severity of the symptoms of disease will also be aggregated to produce a composite COVID-19 severity score. Safety and tolerability assessments will include solicited and unsolicited adverse events (AEs), physical examinations, vital signs, and clinical laboratory tests.

One unblinded interim analysis is planned upon completion of all subjects in Cohort 1. The results of the interim analysis will be reviewed by a safety monitoring team and a recommendation will be made to the sponsor on whether enrollment should proceed for the next cohort at the next planned dose or at a reduced dosing frequency (e.g. once daily). The study is designed to evaluate at least 2 dosing schedules, ascending, or descending based on safety of each previous cohort.

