5.1 Methodological Considerations

General Conventions

SAS software (version 9.4 or higher) will be used for all data analyses and tabulations.

The study is not powered for hypothesis testing. P-values will be considered descriptive and will not be adjusted for multiplicity.

Data for all investigational centers will be pooled for analysis.

Unless specified elsewhere, baseline is defined as the last available measurement prior to administration of study drug. Change from baseline will be calculated as the post-baseline value minus the baseline value.

Summary tables will include the data based upon the protocol scheduled time points. For subjects who are early discontinued from the study, all efficacy assessments captured at the ET visit will be assigned to the nearest protocol scheduled time point.

Visit of Treatment Period	Range*	Target Day
Visit 1 / Baseline (Day 1)	Study Day = 1	Day 1
Visit 2 / Day 2	Study Day = 2	Day 2
Visit 3 / Day 3	Study Day = 3	Day 3
Visit 4 / Day 5 (± 1 day)	Study Day 4 to 6	Day 5
Visit 5 / Day 8 (± 1 day)	Study Day 7 to 9	Day 8

*Study day = date of visit - date of first treatment + 1

Descriptive statistics of continuous variables will include n, mean, standard deviation (SD), median, minimum and maximum. Generally, the minimum and maximum values will be presented to the same decimal precision as the raw values, the mean and median values to one more, and the SD, to two more decimal places than the raw values. Summaries for categorical data will include frequencies and percentages. Percentages will be presented to one decimal place.

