5.5.1 Analysis of Primary Efficacy Endpoint

The primary efficacy endpoint is defined as time-weighted average (TWA) change in log10-transformed viral load by RT-qPCR from baseline to Day 8, where TWA will be derived using the trapezoidal rule:

$$\frac{\sum_{i=a}^{b-1} \{0.5 \times (Y_i + Y_{i+1}) \times (t_{i+1} - t_i)\}}{(t_b - t_a)}$$

Y_i is the change from baseline in log10-transformed viral load by RT-qPCR at Visit i , t is the actual study day at the specified timepoint, a is the baseline visit at Day 1, and b is the Day 8 visit.

At the final analysis, each dose of the RD-X19 device will be compared to sham using an Analysis of Covariance (ANCOVA) model with baseline viral load on log10 scale as a covariate and treatment group as an independent variable.

An example of SAS code for the analysis is as follows:

```
proc glm data=datain;
  class trt;
  model aval = trt base /ss3;
  estimate '4x RD-X19 vs Sham' trt 1 0 -1;
  estimate '7x RD-X19 vs Sham' trt 0 1 -1;
  lsmeans trt /pdiff stderr cl;
run;
```

where AVAL denotes the variable to be analyzed, BASE denotes the covariate baseline value, and TRT denotes treatment group with values 1 for 4 Days RD-X19, 2 for 7 Days RD-X19, and 3 for Sham.

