5.6.4 Other Assessments

Following assessment results will be presented in subject data listing: medical history, physical examination, clinical laboratory evaluations, concomitant medications.

Interim Analysis

Upon completion of all subjects in Cohort 1, an unblinded interim analysis will be conducted focusing on the following evaluations:

- Efficacy:
 - Geometric mean viral load as measured in saliva on day 1, 3, 5 and 8 by RT-qPCR
 - Proportion of subjects demonstrating viral load reduction $\geq 95\%$ on day 3, 5 and 8 by RT-qPCR.
 - Time to alleviation of COVID-19 signs and symptoms
 - Time to sustained alleviation of COVID-19 signs and symptoms
- Safety:
 - All safety tabulations as listed in section 5.6.1 will be assessed as part of the interim analysis.
 - Summary of Treatment Emergent Adverse Events including a review of listings to monitor:
 - Number of study subjects experiencing any Serious Adverse Reaction (SAE).
 - Number of study subject experiencing treatment site reactions, including pain, induration or erythema of the oropharynx or oral mucosa, including the uvula and tongue.
 - Number of study subjects with any laboratory result that is out-of-range using the testing laboratory's institutional standards, including blood, urine and methemoglobin measured by pulse oxymetry.
 - Number of subjects experiencing laryngospasm, bronchospasm or anaphylaxis within 2 hours after use of the RD-X19 Device that is considered related to RD-X19.
 - Number of subjects experiencing an allergic reaction such as generalized urticaria (defined as occurring at three or more body parts) within 72 hours after use of study treatment that is considered related to RD-X19.
 - Number of subjects experiencing Grade 3 TEAE, in the same SOC grouping of PT, considered to be related to RD-X19.

As study subjects in cohort 1 are essentially a separate study, there is no prohibition to sponsor being unblinded for the interim analysis. Cohort 1 subjects are not tied to cohort 2 in any way and unblinding data from cohort 1 has no operational or statistical implications for cohort 2 assessment by sponsor. Study site personnel may not be unblinded to cohort 1 as there is a reasonable possibility that this information could be the basis for bias in the assessment of cohort 2.

To meet above review interest, the following summary tables (treatment groups: 4 Days RD-X19 vs. Sham) and by-subject data listings will be prepared for the interim analysis:

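### The final primary analysis compares each dose with one sham group pooled over two sequential, separately randomised cohorts; state the no-shift assumption, add a concurrent-sham sensitivity model, and correct the SAP's claim that the cohorts are unconnected.

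*Combined protocol and SAP*

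**What the plan says.** SAP 3.1 randomises subjects to RD-X19 or "the sham treatment arm within each cohort in a 2:1 ratio". Cohort 2 follows an unblinded interim analysis held once all Cohort 1 subjects have completed. Treatment lasts four days in Cohort 1 and seven in Cohort 2.

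For the final analysis, SAP 5.5.1 says that "each dose of the RD-X19 device will be compared to sham using an Analysis of Covariance (ANCOVA) model", with baseline log10 viral load as covariate. The example code fits treatment and baseline only, and "TRT denotes treatment group with values 1 for 4 Days RD-X19, 2 for 7 Days RD-X19, and 3 for Sham". Note 2 under the Table 14.2.1.1 shell names the same two terms, and the final shells print one Sham column.

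SAP 5.1 states one kind of pooling in words: "Data for all investigational centers will be pooled for analysis". For the two sham groups, pooling follows from the coding and the shells. I found no sentence giving the assumption it needs (the study-design figures were not available for this check).

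The Interim Analysis text after SAP 5.6.4 says that "Cohort 1 subjects are not tied to cohort 2 in any way" and that "unblinding data from cohort 1 has no operational or statistical implications for cohort 2 assessment by sponsor". The tables listed there include Table 14.2.1.1 for 4 Days RD-X19 against sham in the Cohort 1 ITT population.

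**The concern.** Randomisation supports comparing each dose with the sham subjects of its own cohort. It gives no protection when a dose is compared with shams enrolled in the other cohort, at a different time. The final model gives both kinds of sham subject equal weight.

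If outcomes differ between cohorts for reasons that baseline viral load does not capture, the error enters the two dose estimates with opposite signs. A shift towards faster decline in Cohort 2 would flatter the 7-day dose and penalise the 4-day dose, which could look like a dose response. The reverse shift could hide one. That matters in a study the protocol describes as dose finding.

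The SAP also contradicts itself. The interim text relies on the cohorts being unconnected to permit sponsor unblinding of Cohort 1, while SAP 5.5.1 makes Cohort 1 shams part of the control group for the 7-day dose.

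The interim table gives the 4-day dose one concurrent-sham result for the primary endpoint. No such result is planned for the 7-day dose, and none for either dose at the final analysis.

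**Working it through.** **Inputs.** SAP 3.2: 20 RD-X19 and 10 sham per cohort, 60 in total; 2 x (20 + 10) = 60 reproduces this. Clarification Memorandum #2 allows up to 36 per cohort (30 x 1.2 = 36). The sample size is one of convenience, so there is no planned effect, SD or power to reproduce. Assumptions: residual SD = 1, two-sided 5% level, and d = Cohort 2 minus Cohort 1 mean TWA change after baseline adjustment. The range of d from 0 to 1 SD is illustrative only.

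**Bias.** With no device effect, the pooled sham mean is (10 x 0 + 10 x d)/20 = d/2.
- 4-day estimate: 0 - d/2 = -d/2.
- 7-day estimate: d - d/2 = +d/2.
- The gap between the two estimates is off by d/2 - (-d/2) = d.

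**Precision at target size.**

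| | Pooled sham (20 v 20) | Concurrent sham (20 v 10) |
|---|---|---|
| Variance | 1/20 + 1/20 = 0.10 | 1/20 + 1/10 = 0.15 |
| SE | 0.316 | 0.387 (ratio 1.22) |
| 95% CI half-width | t(56) x 0.316 = 0.63 | t(55) x 0.387 = 0.78 |
| Power for a 1 SD effect | 87% | 72% |
| Difference detectable with 80% power | 0.90 SD | 1.10 SD |

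**Break-even.** Mean squared errors are equal when 0.10 + d²/4 = 0.15, so d² = 0.20 and |d| = 0.447 SD. Below that, pooling has the smaller error; above it, the concurrent comparison does.

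**Coverage.** Simulation of the SAP model used 20,000 runs per value of d, 20:10 in each cohort, a baseline covariate and no device effect:

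| d (SD) | 0 | 0.25 | 0.5 | 0.75 | 1.0 |
|---|---|---|---|---|---|
| Pooled 95% CI coverage | 0.950 | 0.932 | 0.885 | 0.802 | 0.690 |

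Mean bias at d = 0.5 was -0.252 (4-day) and +0.248 (7-day), as the formula predicts. The concurrent-sham model stayed at 0.947 to 0.953 throughout, with absolute bias of 0.005 or less.

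**Can the data test the assumption?** Only the shams can show d. Cohort 2 sham minus Cohort 1 sham has SE sqrt(1/10 + 1/10) = 0.447 SD. Power is about 17% at d = 0.447 and 59% at d = 1, so a non-significant sham difference would not establish that pooling is safe.

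**Overage.** The memorandum gives only the total of 36; a 24:12 split assumes the 2:1 ratio is kept. If Cohort 1 alone uses it, the bias is -10/22 = -0.455d and +12/22 = +0.545d, with break-even at 0.43 SD. If both use it, the bias is again half of d each way and break-even is 0.41 SD.

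**Why one added term is enough.** There are four cohort-by-arm cells. Intercept, two dose terms and cohort make four parameters, so each dose coefficient becomes that dose against its own cohort's sham, with a shared baseline slope. This is the same as a model with four groups.

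**The case against.** The best defence is that pooling is a reasonable choice with so few shams. It doubles each dose's control group and wins on mean squared error for modest shifts; at d = 0.25 SD, coverage is still 93%. Both cohorts share eligibility criteria and a central RT-qPCR laboratory, and the model adjusts for baseline. The study is hypothesis generating, and "P-values will be considered descriptive and will not be adjusted for multiplicity". All of this stands, and it is why the pooled model should remain primary. Site-stratified randomisation does not belong on that list: it balances arms within a cohort and does nothing to make cohorts alike.

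It is also true that the pooling is specified operationally, and that the 4-day dose already has a planned concurrent-sham table. What is missing is the assumption, the 7-day counterpart, and both comparisons at the final analysis.

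Some stronger readings are tempting but unsupported:

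- **That a cohort shift occurred.** Clarification Memorandum #2 shows that recruitment changed when Spanish documents became available during Cohort 1. That is no evidence of a shift in viral-load change.
- **That the sponsor may choose the estimate after unblinding.** SAP section 6 allows example tables, listings and figures to be modified. It does not reopen the model in 5.5.1.
- **That every analysis needs reworking.** The code line "lsmeans trt /pdiff stderr cl" would print a 4-day against 7-day difference, but Table 14.2.1.1 does not report it. Duplicated log-rank tests and sham-by-cohort columns throughout go beyond what the problem needs.

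**Conclusion.** The concern holds in a limited form. At target enrolment, half of each dose's controls in the final primary analysis are non-concurrent, and any baseline-adjusted cohort shift passes into the two estimates at half its size with opposite signs. The consequence is a possibly biased estimate and a confidence interval that may under-cover. A reader might infer a loss of confirmatory error control, but the SAP makes no confirmatory claim to lose.

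How much this matters depends on d, which the documents do not give. Below about 0.45 SD pooling is the better estimator, and above it the concurrent comparison is. The trial's shams are too few to show which case applies, so both results should be reported.

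The contradiction does not depend on d. Cohort 1 shams supply 10 of the 20 planned controls for the 7-day dose, so the interim text is wrong to deny any statistical link between the cohorts.

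**What to change.** 1. In SAP 5.5.1, keep the pooled-sham ANCOVA as primary and state that it assumes no cohort shift in TWA change after baseline adjustment.
2. Before Cohort 2 is unblinded, pre-specify one sensitivity model for the primary endpoint that adds cohort as a class variable: `model aval = trt cohort base`. The existing dose contrasts then give 4-day against Cohort 1 sham and 7-day against Cohort 2 sham. Report these beside the pooled results in Table 14.2.1.1.
3. Correct the Interim Analysis text to say that Cohort 1 shams contribute to the pooled comparison for the 7-day dose.

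The cost is one model, its table rows and two short text changes. Listing 16.2.6.4 already carries cohort beside each subject's TWA value, so no new data are needed. The sensitivity estimate is less precise (SE 0.387 against 0.316 SD; 95% CI half-width 0.78 against 0.63 SD), but it leaves the primary result unchanged.

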5.5.2 Analysis of Secondary Efficacy Endpoints

The following 6 secondary efficacy endpoints will be summarized using descriptive statistics by visit, as appropriate:

- log10-transformed Viral load as measured in saliva by RT-qPCR at each visit by RT-qPCR
- proportion of subjects with $\geq 95\%$ reduction in SARS-CoV-2 viral load by RT-qPCR at each visit
- time to clearance of viral infection in saliva via RT-qPCR
- proportion of subjects demonstrating clearance of viral infection via RT-qPCR at Day 8/ET visit
- COVID-19 composite severity score at each visit
- time to alleviation of COVID-19 symptoms, defined as the number of hours from the first dose to the first time when all eight symptoms had been assessed by the subject as none (0) or mild (1)
- time to sustained alleviation of COVID-19 symptoms, defined the number of hours from the first dose to the time when all eight symptoms had been assessed by the subject as none (0) or mild (1) and no single symptom reoccurs later at a level above mild (1).

Both time to alleviation of COVID-19 symptoms and time to sustained alleviation of COVID-19 symptoms will be derived from self-assessment by study subjects and recorded on the subjects' diary cards.

For log10-transformed viral load data, geometric means will be computed by exponentiating (base 10) the group means of the log10-transformed viral load. Time-to-event variables will be evaluated using the Kaplan-Meier method and p-values for treatment comparison will be provided via log rank test.

